#### **4.2.3.2 *Exploratory objectives***

Perform analyses of tumor infiltrating lymphocytes (TILs) to identify changes in functional markers in response to the addition of itacitinib to pembrolizumab. This study will be a pilot feasibility study of performing multiparametric analysis of TILs, particularly CD8+ T cells, from patients with metastatic NSCLC using approaches such as flow cytometry and multicolor immunohistochemistry.

Given the potential role for chronic interferon signaling as well as other inflammatory cytokines regulated by JAK/STAT signaling in impairing T cell function, we anticipate that response to itacitinib and pembrolizumab will be associated with 1) sustained activation of PD1+ T cells after an initial proliferative burst as measured by Ki67, 2) high pre-treatment interferon levels that is suppressed during treatment, and 3) high gene expression levels of resistance-associated ISGs. We hypothesize that subjects failing to respond to treatment will show initial proliferative burst in PD1+ T cells that is not sustained despite continued pembrolizumab, and 2) decreased expression of various other markers of T cell activation.

Additionally, deep sequencing of the T cell receptor (TCR) in tumor and blood will be performed as feasible to identify clones that expand after treatment and monitor their persistence over time. These are non-biased approaches to identify tumor reactive T cells in subjects where the specific neoantigen is not known.

## **5.0 METHODOLOGY**

### **5.1 *Entry Criteria***

#### **5.1.1 *Inclusion Criteria***

1. Stage IV or metastatic non-small cell lung cancer (NSCLC)
2. Provide written informed consent for the trial.
3. Patients  $\geq$  18 years of age
4. Tumor PD-L1 $\geq$  50% as assessed by the PD-L1 IHC 22C3 pharmDx assay (Dako North America).
5. Subject must have adequate tumor burden at a safely accessible site for biopsy.  
NOTE: If sites chosen for biopsy were previously irradiated, there must be evidence of tumor growth/viable tumor as assessed by the investigator.
6. At least one measurable lesion according to Response Evaluation Criteria in Solid Tumors (RECIST) v1.1
7. ECOG performance status 0 or 1
8. Adequate organ function as defined in **Table 1**

CONFIDENTIAL

This material is the property of the University of Pennsylvania. Do not disclose or use except as authorized in writing by the study sponsor.

**Table 1** Adequate Organ Function Laboratory Values

System	Laboratory Value
Hematological	
Absolute neutrophil count (ANC)	≥1,250/mcL
Platelets	≥100,000/mcL
Hemoglobin	≥9 g/dL or ≥5.6 mmol/L
Renal	
Serum creatinine OR Measured or calculated a creatinine clearance (GFR can also be used in place of creatinine or CrCl)	≤1.5 X upper limit of normal (ULN) OR ≥50 mL/min for subject with creatinine levels > 1.5 X institutional ULN
Hepatic	
Serum total bilirubin	≤ 1.5 X ULN OR Direct bilirubin ≤ ULN for subjects with total bilirubin levels > 1.5 ULN
AST (SGOT) and ALT (SGPT)	≤ 2.5 X ULN OR ≤ 5 X ULN for subjects with liver metastases

aCreatinine clearance should be calculated per institutional standard.

9. Subjects of reproductive potential must agree to use acceptable birth control methods as described in protocol **Section 5.6.2**.

### 5.1.2 **Exclusion Criteria**

1. Sensitizing mutations in Epidermal growth factor receptor (*EGFR*) or anaplastic lymphoma kinase (*ALK*) or ROS1 proto-oncogene receptor tyrosine kinase (*ROS1*) translocations
2. Currently participating in or has participated in a study of an investigational agent or anticipated use of an investigational device within 4 weeks of the first dose of study treatment.
3. Untreated symptomatic central nervous system (CNS) metastases and/or carcinomatous meningitis.
4. Received prior systemic cytotoxic chemotherapy, biologic therapy, targeted therapy or immunotherapy for incurable (metastatic) NSCLC.
5. Diagnosis of immunodeficiency within 7 days prior to eligibility confirmation by the physician-investigator.
6. Prior monoclonal antibodies used for the treatment of NSCLC within 4 weeks prior to eligibility confirmation by the physician-investigator, or individuals who have not recovered (i.e., ≤ Grade 1 or at baseline) from adverse events due to agents administered more than 4 weeks earlier.

CONFIDENTIAL

This material is the property of the University of Pennsylvania. Do not disclose or use except as authorized in writing by the study sponsor.

7. Known additional malignancy that is progressing or requires active treatment. Exceptions include basal cell carcinoma of the skin, squamous cell carcinoma of the skin, non-invasive bladder tumors, or in situ cervical cancer
8. Active autoimmune disease requiring systemic immunosuppressive treatment within the past 3 months prior to eligibility confirmation by the physician-investigator. Subjects that require intermittent use of steroid-containing bronchodilators or local steroid injections or topical steroid medications are not excluded from the study. Subjects with hypothyroidism stable on hormone replacement or Sjogren's syndrome are not excluded from the study.
9. Interstitial lung disease or history of pneumonitis that has required oral or IV steroids
10. Active infection requiring systemic therapy with IV antibiotics
11. History or current evidence of any condition, therapy, or laboratory abnormality that might confound the results of the trial, interfere with the subject's participation for the full duration of the trial, or is not in the best interest of the subject to participate, in the opinion of the treating investigator.
12. Known psychiatric or substance abuse disorders that would interfere with cooperation with the requirements of the trial.
13. Pregnant or breastfeeding women
14. Prior therapy with an anti-PD-1, anti-PD-L1, anti-PD-L2, anti-CD137, or anti-Cytotoxic T-lymphocyte-associated antigen-4 (CTLA-4).
15. Known history of Human Immunodeficiency Virus (HIV) (HIV 1/2 antibodies).
16. Known active Hepatitis B (e.g., HBsAg positive or HBV DNA detectable) or Hepatitis C (e.g., HCV RNA [qualitative] is detected).
17. Anticipated receipt of any live vaccine within 30 days prior to the first dose of trial treatment.

Note: For the purposes of determining eligibility above, enrollment is defined as the date of subject consent.

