### **5.4.2 Prohibited Concomitant Medications**

Subjects are prohibited from receiving the following therapies during the Screening and Treatment Phase (including retreatment for post-complete response relapse) of this trial:

- Systemic corticosteroid therapy or any other form of immunosuppressive therapy is prohibited within 7 days prior to study treatment. (Nasal or oral inhalers are permissible). Physiologic replacement doses of steroids (mineralocorticoid or less than or equal to a prednisone 10 mg daily dose) will also be permitted.

CONFIDENTIAL

This material is the property of the University of Pennsylvania. Do not disclose or use except as authorized in writing by the study sponsor.

- Anti-cancer systemic chemotherapy or biological therapy
- Immunotherapy not specified in this protocol
- Investigational agents other than pembrolizumab and itacitinib
- Radiation therapy
  - Note: Radiation therapy to a symptomatic solitary lesion or to the brain may be allowed per physician-investigator discretion, but would be regarded as a disease progression event for the primary endpoint. However as per Section 4.2.2, subjects may continue to receive pembrolizumab at the physician-investigator's discretion if the subject continues to benefit clinically from treatment.
- Live vaccines within 30 days prior to the first dose of trial treatment and while participating in the trial. Examples of live vaccines include, but are not limited to, the following: measles, mumps, rubella, chicken pox, yellow fever, rabies, BCG, and typhoid (oral) vaccine. Seasonal influenza vaccines for injection are generally killed virus vaccines and are allowed; however intranasal influenza vaccines (e.g. Flu-Mist®) are live attenuated vaccines and are not allowed.
- Glucocorticoids, in excess of physiologic doses (prednisone >10 mg per day equivalent), for any purpose other than an abbreviated course to modulate symptoms from an event of clinical interest of suspected immunologic etiology.
- CYP3A4 inhibitors and dual CYP3A4/2C9
- Fluconazole (>200mg doses)

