###### 7.1.1.2 *Inclusion/Exclusion Criteria*

All inclusion and exclusion criteria will be reviewed by the physician-investigator to ensure that the subject qualifies for the trial.

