###### 7.1.1.3 *Medical History*

A medical history will be obtained by the investigator or qualified designee. Medical history will include all active conditions, and any condition diagnosed within the prior 10 years that are considered to be clinically significant by the Investigator. Details regarding the disease

CONFIDENTIAL

This material is the property of the University of Pennsylvania. Do not disclose or use except as authorized in writing by the study sponsor.

for which the subject has enrolled in this study will be recorded separately and not listed as medical history.

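### Exclusion 5 as written does not reach an immunodeficiency diagnosed more than 7 days before eligibility confirmation; apart from known HIV, only the discretionary exclusion 11 would catch it

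*Combined protocol and SAP*

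**What the plan says.** Section 5.1.2, no. 5, excludes on "Diagnosis of immunodeficiency within 7 days prior to eligibility confirmation by the physician-investigator". It gives no rationale for the 7 days and does not define immunodeficiency.

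Four other provisions bear on the same patients:

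- No. 15 excludes "Known history of Human Immunodeficiency Virus (HIV) (HIV 1/2 antibodies"), with no time limit.
- No. 8 excludes "Active autoimmune disease requiring systemic immunosuppressive treatment within the past 3 months prior to eligibility confirmation by the physician-investigator".
- No. 11 excludes on "History or current evidence of any condition, therapy, or laboratory abnormality that might confound the results of the trial", or where a condition would interfere with full participation or "is not in the best interest of the subject to participate, in the opinion of the treating investigator".
- Section 5.4.2, whose list covers the screening and treatment phases, states: "Systemic corticosteroid therapy or any other form of immunosuppressive therapy is prohibited within 7 days prior to study treatment". Inhalers and physiologic steroid replacement are excepted.

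Section 7.1.1.2 provides that "All inclusion and exclusion criteria will be reviewed by the physician-investigator to ensure that the subject qualifies for the trial". Section 7.1.1.3 provides that "Medical history will include all active conditions, and any condition diagnosed within the prior 10 years", subject to clinical significance.

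**The concern.** A time limit on the date of diagnosis separates two patients with the same condition by when it was found, not by whether they have it. The patient diagnosed last week is barred; the patient diagnosed last year is not. That is hard to square with an exclusion that appears meant to keep immunodeficient patients away from an anti-PD-1 antibody combined with a JAK1 inhibitor.

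What is at stake is mainly safety and interpretability. Tolerability is one of the two primary endpoints (Section 8.2.1). The protocol's own dose-modification table for itacitinib (Table 3) has rows for Grade 3-4 infection and for febrile neutropenia. The biomarker hypothesis in Section 8.2.1 predicts increased T-cell activation in peripheral blood, and the exploratory predictions in Section 4.2.3.2 turn on the behaviour of PD1+ T cells. Immune competence at baseline bears on all of these.

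**Working it through.** No formula applies and the plan gives no figure to reproduce. The check is a literal reading of exclusion 5 against the other entry criteria, the prohibited-medication rules and the screening procedures.

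**Step 1: what no. 5 covers.** Let d be the number of days from diagnosis to eligibility confirmation. The criterion is met when d is between 0 and 7 and not met when d is greater than 7. At d = 5 the patient is excluded; at d = 8 or d = 365 the patient is not.

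**Step 2: what the other provisions cover.**

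| Patient | Provision | Outcome |
|---|---|---|
| Immunodeficiency diagnosed within the 7 days | No. 5 | Excluded |
| Known HIV, any duration | No. 15 | Excluded |
| Active autoimmune disease needing systemic immunosuppression in the past 3 months | No. 8 | Excluded |
| Systemic immunosuppressive therapy within 7 days before study treatment | Section 5.4.2 | Prohibited, with stated exceptions |
| Other immunodeficiency diagnosed more than 7 days before, off immunosuppressants | No. 11 only | Depends on the investigator's opinion |

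The last row is the gap.

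**Step 3: is the window likely to be misplaced?** Compare the look-back windows in Section 5.1.2:

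- No. 2: 4 weeks, attached to investigational-study participation.
- No. 6: 4 weeks, attached to prior monoclonal antibodies.
- No. 8: 3 months, attached to immunosuppressive treatment.
- No. 17: 30 days, attached to a live vaccine.
- No. 5: 7 days, attached to a diagnosis.

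Only no. 5 ties its window to the date on which a condition was named; the other four tie theirs to an exposure. Section 5.4.2 has the same 7 days and attaches them to therapy. Its anchor differs, however: study treatment there, eligibility confirmation in no. 5. The pattern fits wording lost in drafting, but the two rules govern different things and do not contradict each other, so it is an inference.

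**Step 4: do the procedures close the gap?** The medical history would record a long-standing active immunodeficiency, so the investigator would see it. Recording is not excluding, though: Section 7.1.7.1 defines the entry requirements as those in Section 5.1. The monitors in Section 12.1 check subjects against the inclusion and exclusion criteria, and enrolling such a patient would not breach no. 5.

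**Step 5: effect on the design.** The stated false-positive error (0.100) and power (0.906) follow from the stage sizes (11, 30 and 48 cumulative), the response cut-offs and the assumed response rates (35% and 55%). Exclusion 5 enters none of these, nor the sample size.

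**The case against.** The strongest reply is that such a patient would still be seen and could still be turned away. No. 11 has no time limit, covers any condition, and lists as grounds the very harms at issue: confounded results and a subject's best interest. The physician-investigator reviews every criterion. This stands as a partial safeguard. It does not make no. 5 work, because no. 11 depends on opinion and two investigators could decide the same case differently. A specific criterion limited to 7 days may also be taken to mean that older diagnoses are acceptable.

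A site might also read no. 5 charitably, as covering anyone who carries the diagnosis during those 7 days. If that is the intent, the window does almost no work and the sentence should say what it means.

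Three stronger readings are tempting, and the documents do not support them.

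- A reader might infer that any patient with long-standing immunodeficiency is eligible. Known HIV is barred by no. 15, and for other conditions eligibility is conditional on no. 11.
- A reader might infer that patients on recent immunosuppression slip through before dosing. They are addressed by no. 8, by Section 5.4.2 during screening, and by the 28-day prior-medication review in Section 7.1.1.4.1, which includes washout requirements. No. 11 also names therapy as a ground.
- A reader might infer that Section 5.4.2 proves where the window belongs. It makes a drafting slip plausible and no more.

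Nor is there a case that the trial's conclusion is biased towards success. If immunodeficient subjects responded less well, they would lower the observed response rate, which does not raise the false-positive error.

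**Conclusion.** The point holds in a limited form. Exclusion 5, followed literally, misses immunodeficiency diagnosed more than 7 days before eligibility confirmation. Outside known HIV, no explicit and automatic criterion fills that gap for a patient off immunosuppressants; no. 11 may fill it, at the investigator's discretion.

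The size cannot be computed, because the documents give no frequency of immunodeficiency in this population. That few subjects would be affected is an assumption, though a reasonable one for a trial of up to 48 evaluable subjects. The conclusion rests on the literal wording and on no statistical input. The defect is one of drafting in a safety criterion. It deserves correction because it is operative and cheap to repair, not because it threatens the primary analysis.

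**What to change.** In the next amendment, reword exclusion 5 so that its time window no longer places established immunodeficiency outside the criterion, and state its intended scope: which conditions it covers, and whether it is meant to address a condition, a therapy or both. Then reconcile its window and its anchor date with Section 5.4.2, and make its relation to nos. 8, 11 and 15 explicit so that each patient type falls under a known rule.

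The sponsor should decide what the 7 days were meant to qualify. The documents do not settle this, so no particular steroid or immunosuppressant window is proposed here as an entry rule.

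The cost is about one eligibility sentence, with a matching change to any eligibility checklist that repeats it. Sample size, stage boundaries and analyses are untouched. If subjects are already enrolled, reviewing their recorded medical histories for immunodeficiency would show whether the gap has had any effect.

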## **5.2 Enrollment**

The Subject Number consists of the Protocol Number with a sequential subject number affixed to it. Assignment of subject numbers will occur at the time of consent and occur in ascending order (i.e. 09517-01, 09517-02, etc). No numbers will be omitted. Subject numbers will thereafter be used on all study documentation.

At the time a subject consents to participate in this study, a Consent Notification Form should be completed. When eligibility of the subject is confirmed by a physician-investigator, an Enrollment Notification should be completed. Both completed forms should be emailed in real-time to the Protocol Monitoring and Sponsor Project Manager.

CONFIDENTIAL

This material is the property of the University of Pennsylvania. Do not disclose or use except as authorized in writing by the study sponsor.

### 5.3 Study Drugs

The treatments to be used in this trial are outlined below in **Table 2**.

**Table 21: Trial Treatment**

Drug	Dose/Potency	Dose Frequency	Route of Administration	Regimen	Use
Pembrolizumab	200 mg	Q3W	IV infusion	Day 1 of each 3-week cycle; up to 4 study treatment cycles*	Per label- with the exception of the drug being administered with itacitinib
Itacitinib (INCB039110)	200 mg	Once Daily	Oral	Daily for cycles 3-4 (q3 weeks); up to 42 days of therapy	Investigational

The pembrolizumab dosing interval may be modified as per package insert.  
\*If the PI considers it beneficial for the subject, a fifth cycle may be administered prior to EOS visit.

#### 5.3.1 Dose Selection/Modification

##### 5.3.1.1 Dose Selection

The rationale for selection of doses to be used in this trial is provided in [Section 4.0](#) – Background and Rationale.

##### 5.3.1.2 Dose Modifications

###### **Pembrolizumab**

Please refer to the pembrolizumab package insert.

CONFIDENTIAL

This material is the property of the University of Pennsylvania. Do not disclose or use except as authorized in writing by the study sponsor.

## Itacitinib

**Table 3: Dose modification guidelines for itacitinib-related adverse events.**

Toxicity	Grade	Hold Treatment (Y/N)	Timing for restarting treatment 	Dose/Schedule for restarting treatment	Discontinue itacitinib (after consultation with the Sponsor Medical Director) 
Hematological Toxicity	1, 2	No	N/A	N/A	N/A
	3, 4	Yes	Toxicity improves to Grade 0-2 or baseline	Reduce itacitinib by 1 dose level (100 mg daily)  If second dose reduction is necessary subject will be discontinued from itacitinib treatment.	Toxicity does not resolve within 2 weeks of last dose.  If second dose reduction is necessary subject will be discontinued from itacitinib treatment.
Thrombocytopenia with bleeding	1, 2	No- but dose reduce	N/A	Reduce itacitinib by 1 dose level (100 mg daily)  If second dose reduction is necessary subject will be discontinued from itacitinib treatment.	If second dose reduction is necessary subject will be discontinued from itacitinib treatment.
	3, 4	Yes	Toxicity improves to Grade 0-2 or baseline	Hold itacitinib until count recovery.  If second dose hold is necessary subject will be discontinued from itacitinib treatment.	Toxicity does not resolve within 2 weeks of last dose.  If second dose hold is necessary subject will be discontinued from itacitinib treatment.

CONFIDENTIAL

This material is the property of the University of Pennsylvania. Do not disclose or use except as authorized in writing by the study sponsor.

Toxicity	Grade	Hold Treatment (Y/N)	Timing for restarting treatment 	Dose/Schedule for restarting treatment	Discontinue itacitinib (after consultation with the Sponsor Medical Director) 
Febrile neutropenia	3	Yes	N/A	N/A	Discontinue itacitinib
Infection	3,4	Yes	Completion of IV antibiotics	Reduce itacitinib by 1 dose level (100 mg daily)	Toxicity does not resolve with typical antibiotic course
Non-hematological toxicity  Note: Exceptions to be treated similar to grade 1 toxicity 

Grade 2 alopecia

Grade 2 fatigue

	1	No	N/A	N/A	N/A
	2	Consider withholding for clinically significant symptoms	Toxicity improves to Grade 0-1 or baseline	Same dose and schedule	N/A
	3, 4	Yes	Toxicity improves to Grade 0-1 or baseline	Reduce itacitinib by 1 dose level (100 mg daily)  If second dose reduction is necessary subject will be discontinued from itacitinib treatment.	Toxicity does not resolve within 2 weeks of last dose.  If second dose reduction is necessary subject will be discontinued from itacitinib treatment.
Hepatic Toxicity	Bilirubin $\geq$ 2 x ULN AND Grade 3 AST/ALT ( $\geq$ 3 x ULN)	Yes	N/A	N/A	Discontinue itacitinib

\* N/A = Not applicable

1- Missed doses will not be made up. The subject may receive up to 42 days of itacitinib therapy.

2- If a subject discontinues itacitinib therapy, they may continue on pembrolizumab treatment and may remain on study.

### 5.3.2 Timing of Dose Administration

Trial treatment should be administered on Day 1 of each cycle after all procedures/assessments have been completed as detailed on the Trial Flow Chart ([Section 6.0](#)). Trial treatment may be

CONFIDENTIAL

This material is the property of the University of Pennsylvania. Do not disclose or use except as authorized in writing by the study sponsor.

administered up to 3 days before or after the scheduled Day 1 of each cycle due to administrative reasons.

All trial treatments will be administered on an outpatient basis.

Pembrolizumab will be administered q3 weeks as a 30 minute IV infusion. Up to 4 cycles of pembrolizumab will be administered as part of this study. If the PI considers it beneficial for the subject, a fifth cycle may be administered prior to EOS visit. Pembrolizumab treatment cycle intervals may be increased due to toxicity as per package insert. Sites should make every effort to target infusion timing to be as close to 30 minutes as possible. However, given the variability of infusion pumps, a window of +/- 10 minutes is permitted.

Itacitinib will be administered daily starting at Cycle 3/Day 1 and continue for a total of 6 weeks (42 days). Itacitinib should be taken orally by the subject at the prescribed dose- 200 mg QD (2 x 100 mg tablets). If dose reductions are required due to toxicity, the prescribed dose may be reduced to 100 mg QD (1 x 100 mg tablet). Itacitinib should be taken with water, and may be taken without regard to food. If itacitinib doses are missed due to toxicity (per [Table 3](#)) or if vomiting occurs, these missed doses will not be made up.

